11.7.6 Vision Symptom Questionnaire

Vision symptom questionnaire data will be summarized for the Post-Amendment 3 safety population by visit and by dose level for the open-label period.

11.7.7 R- and S-Oxybutynin and N-desethyloxybutynin Plasma Concentrations

Plasma concentration data for *oxybutynin* and DEO plasma concentrations for the R-isomer, S-isomer, and R+S as well as the ratio of DEO to *oxybutynin* will be summarized for the pharmacokinetic population by visit. Summaries will be provided overall and for each age group and sex.

Linear *or nonlinear* regression, *as appropriate*, will be used to *investigate the* relationship between the CFB in the efficacy variables and plasma concentrations, age and plasma concentrations, weight and plasma concentrations, and *body mass index* and plasma concentrations for each visit.

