This study was initiated as a double-blind, placebo-controlled study with an open-label extension, and amended to enroll patients under only open-label treatment. Prior to Amendment 3, patients aged 6 years to < 17 years were randomly assigned 1:1 to receive double-blind oxybutynin chloride gel or placebo gel for 6 weeks, followed by an open-label, 8-week period to generate safety data. All patients began treatment with 0.75 g of gel/day for 2 weeks. Patients then returned to the clinic for a potential dose titration and at this time their dose could have been adjusted up to 1 g/day, down to 0.5 g/day, or remained the same at 0.75 g/day. The determination of dose was based on the investigator's clinical judgment and assessment of the patient's bladder symptoms and treatment side effects. Dose titration was permitted only once during the entire 6-week double-blind, placebo-controlled period. Patients continued blinded treatment for 4 additional weeks until the end of the double-blind treatment period.

Post-Amendment 3, the study dose-titration study in pediatric patients, ages 3 years to < 17 years, with detrusor overactivity associated with a neurological condition. Efforts will be made to enroll a greater number of patients from the ages of 3 years to < 6 years. Patients must be suitable candidates for anticholinergic therapy and must be using clean intermittent catheterization (CIC) for bladder control. The study will include a screening period from Day -13 to Day -5 and a 14-week open-label treatment period. The expected duration of the study for each patient will be up to 16 weeks. No changes were made in the starting dose, compared to the Pre-Amendment 3 study design, in that all patients will begin treatment with 0.75 g of gel/day for 2 weeks. Patients will then return to the clinic for a potential dose titration and at this time their dose may be adjusted up to 1 g/day, down to 0.5 g/day, or remain the same at 0.75 g/day, depending on individual response and tolerability. The determination of dose will be based on the investigator's clinical judgment and assessment of the patient's bladder symptoms and treatment side effects. Dose titration will be permitted only once during the entire 14-week treatment period. Patients will continue the adjusted dose for 12 additional weeks until the end of the open-label treatment period.

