9.8.1 Determination of R- and S- Oxybutynin and N-desethyloxybutynin Plasma Concentrations

Venous blood samples will be collected at Visits 3, 4, 5, and 6 (*Pre-Amendment 3*) or Visits C, D, and F/ET (Post-Amendment 3) for determination of oxybutynin and N-desethyloxybutynin plasma concentrations.

Blood samples (approximately 6 mL) will be collected into labeled purple top, EDTA collection tubes. They will be processed for plasma according to the standard procedure at the study site and the resulting plasma sample will be divided into 2 equal aliquots for storage at -20° C. The samples will be sent to a contract laboratory for analysis of R- and S-oxybutynin and N-desethyloxybutynin concentrations by a validated bioanalytical method.

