11.2 Analysis Populations and Databases

Statistical analysis and data tabulation will be performed using *data from the open-label period for patients enrolled after Amendment 3 and the data from the double-blind and open-label periods for patients enrolled prior to Amendment 3 in* the following patient populations unless specified otherwise:

- Safety populations:
 - Post-Amendment 3 open-label safety population
 - Pre-Amendment 3 double-blind safety population
 - Pre-Amendment 3 open-label safety population
 - Combined open-label safety population (Pre- and Post-Amendment 3)
- Intent-to-treat (ITT) populations:
 - Combined ITT population (Pre- and Post-Amendment 3; primary efficacy analysis population)
 - Post-Amendment 3 ITT population
 - Pre-Amendment 3 ITT population

- Per-protocol (PP) populations:
 - Post-Amendment 3 PP population
 - Pre-Amendment 3 PP population
- PK populations:
 - Post-Amendment 3 PK population
 - Pre-Amendment 3 PK population
 - Combined PK population (Pre- and Post-Amendment 3)

The *Post-Amendment 3 open-label* safety population is defined as all *patients* who receive at least *1* dose of *study treatment in* the open-label period *after Amendment 3*.

The Pre-Amendment 3 double-blind safety population is defined as all patients who receive at least 1 dose of study treatment in the double-blind period before Amendment 3.

The Pre-Amendment 3 open-label safety population is defined as all patients who receive at least 1 dose of study treatment in the open-label period before Amendment 3.

The combined open-label safety population is defined as all patients who receive at least 1 dose of study treatment in the open-label period before or after Amendment 3.

The primary efficacy analysis populations will be the *Post-Amendment 3* ITT population *and the Pre-Amendment 3 ITT population*.

The combined ITT population will include all patients who have a baseline value for the primary efficacy variable in the Post-Amendment 3 open-label period or all randomized patients who have a baseline value for the primary efficacy variable in the Pre-Amendment 3 double-blind period.

The Post-Amendment 3 ITT population will include all randomized patients who have a baseline value for the primary efficacy variable in the Post-Amendment 3 open-label period.

The *Pre-Amendment 3* ITT population will include all randomized patients who have a baseline value for the primary efficacy variable *in the Pre-Amendment 3 double-blind period*.

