The *Pre-Amendment 3* PP population will include all *patients* in the *Pre-Amendment 3* ITT population who complete the *double-blind* treatment period of the study and who are without significant protocol violations.

The Post-Amendment 3 PP population will include all patients in the Post-Amendment 3 ITT population who complete the Post-Amendment 3 open-label treatment period of the study and who are without significant protocol violations.

The PK population will include all *patients* who have at least 1 sample draw for plasma concentrations. The PK population will only be used in the summary statistics and analyses of the *PK* data.

Additionally, 2 types of visits are defined for the purposes of analysis and summary:

- Observed cases (OC)
- Last observation carried forward (LOCF)

The OC visits are defined to be those assessment values observed at each scheduled visit. All applicable efficacy and safety variables will be summarized using the OC visits.

The LOCF visit is defined as the last data recorded for each efficacy variable. This visit will be *designated as* Week 6 (LOCF). *The Week 6 (LOCF) visit will be defined for the Post-Amendment 3 open-label period and the Pre-Amendment 3 double-blind period* and will only be used to summarize efficacy data. The LOCF visit provides missing value imputation for *patients* who do not complete the *open-label treatment period (Post-Amendment 3) or the double-blind treatment period (Pre-Amendment 3)* of the study and will include all *patients* in the *corresponding* ITT population.

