11.7.4 Urodynamic Variables

Urodynamic variables will be summarized for the *Pre-Amendment 3 double-blind and Post-Amendment 3* safety populations. *Results will be presented* by treatment group and visit and by treatment group, dose level, and visit for the *Pre-Amendment 3 double-blind* period *and by oxybutynin chloride gel only and visit for the post-Amendment 3 open-label period* using descriptive statistics (mean, 25th percentile, median, 75th percentile, SD, SEM, minimum, maximum, and number of *patients*) for continuous variables and frequency distributions (number and percentage of *patients*) for categorical variables. Summaries will be provided overall and for each age group and *sex*. In addition, descriptive statistics will be presented for change from baseline (baseline is defined as Week 0) for continuous urodynamic variables.

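### The protocol's PK rule admits placebo patients and has no dose or treatment term, so Pre-Amendment 3 and Combined concentration summaries are diluted and post-titration samples mix doses

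*Protocol*

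**What the plan says.** **PK analysis.** Protocol 11.7.7 covers concentrations of oxybutynin and DEO and the metabolite-to-parent ratio. These data "will be summarized for the pharmacokinetic population by visit. Summaries will be provided overall and for each age group and sex". Regressions at each visit relate concentration to change in the efficacy variables, then "age and plasma concentrations, weight and plasma concentrations, and" finally body mass index. Sex is a summary factor only. Neither dose nor treatment group appears.

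**PK population.** Protocol 11.2 takes all patients "who have at least 1 sample draw for plasma concentrations" and lists Pre-Amendment 3, Post-Amendment 3 and Combined versions. None is limited to active gel. SAP Table 5-1 defines no PK population, and SAP section 4 leaves PK to a separate plan.

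**Sampling and dose.** For Pre-Amendment 3, Protocol 9.8.1 says "Venous blood samples will be collected at Visits 3, 4, 5, and 6". The schedule in SAP Appendix 1 places these at Weeks 1, 2, 4 and 6, all double-blind, with no draw in the open-label extension. Those patients "were randomly assigned 1:1 to receive double-blind oxybutynin chloride gel or placebo gel for 6 weeks" (Protocol synopsis). On dose, the synopsis says "All patients began treatment with 0.75 g of gel/day for 2 weeks"; one titration to 0.5, 0.75 or 1 g/day was then possible. Post-Amendment 3 draws are at Visits C, D and F (Weeks 2, 6 and 14). Protocol 9.1 puts the Visit C titration after that visit's assessments.

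**Neighbouring sections.** Protocol 11.7.5 (anticholinergic questionnaire) and 11.7.6 (vision questionnaire) name dose level. Protocol 11.7.4 presents urodynamics "by treatment group and visit and by treatment group, dose level, and visit for the" Pre-Amendment 3 double-blind period, but does not split the Post-Amendment 3 urodynamics by dose.

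**The concern.** Concentration is the outcome most directly tied to dose, yet it is the one summarised without reference to dose or to whether the patient received drug at all. PK in children is a secondary objective (Protocol 8.2). Amendment 3 extended enrolment down to age 3 at the same starting dose, so the age and weight analyses are where the trial examines exposure by body size.

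Two separate problems follow from the wording. Placebo patients add values at or near zero, which pulls down means and flattens slopes. They also have no meaningful DEO to oxybutynin ratio. Second, after titration the active samples span a two-fold dose range. Dose was chosen on bladder symptoms and side effects, so it is not random with respect to patient characteristics.

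**Working it through.** **1. The plan's own sizing figure.** Protocol 11.1 and SAP 5.1.2 give a difference of 20, SD 28, 48 per arm and 93% power, or 90% with 10% dropout. The standardised difference is 20 / (28 × √(2/48)) = 3.50. At two-sided 0.05 (taken from the 95% intervals in SAP 5.1.1.1.3), noncentral-t power is 93.4%; with 43.2 per arm it is 90.7%. Both agree with the plan. The PK point uses only the planned counts: 48 + 48 Pre-Amendment 3 and at least 25 Post-Amendment 3.

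**2. Active doses present at each draw (g/day; 0 = placebo).**

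| Draw | Pre-Amendment 3 | Post-Amendment 3 | Combined |
|---|---|---|---|
| Week 1 | 0, 0.75 | none | Pre only |
| Week 2 | 0, 0.75 | 0.75 | 0, 0.75 |
| Week 4 | 0, 0.5, 0.75, 1 | none | Pre only |
| Week 6 | 0, 0.5, 0.75, 1 | 0.5, 0.75, 1 | 0, 0.5, 0.75, 1 |
| Week 14 | none | 0.5, 0.75, 1 | Post only |

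**3. Placebo share and means.**
- Pre-Amendment 3: 48/96 = 50%.
- Combined (Weeks 2 and 6): 48/(96 + 25) = 48/121 = 39.7%.
- Post-Amendment 3: 0/25 = 0%.

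If placebo concentrations are 0, pooled mean = (1 − placebo share) × active mean. That gives 50% of the active mean Pre-Amendment 3 and 60.3% Combined. The numbers actually enrolled before the amendment are not in the documents. If only half of the 96 had been enrolled, the Combined share would be 24/(48 + 25) = 32.9% and the mean 67.1%. The Pre-Amendment 3 share stays near 50% at any enrolment.

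Randomisation was stratified by age and weight (Protocol 9.4.3). Within Pre-Amendment 3, placebo should therefore be spread evenly over size, and the slope halves as well. The simulation described in step 5, with 48 placebo patients added to 48 active, gives −0.76 at Week 2 against about −1.5 for active patients only.

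**4. Age in the Combined population.** Children aged 3 to <6 were enrolled only on open-label gel, so their placebo share is 0. If k of the 25 Post-Amendment 3 patients are that age, the share among older patients is 48/(121 − k): 48/120 = 40% at k = 1 and 48/96 = 50% at k = 25. Suppose active concentrations were the same at every age. The youngest group would then show 1/0.60 = 1.67 to 1/0.50 = 2.00 times the mean of the older patients, purely from placebo.

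**5. Dose after titration.** The documents give no relation between dose and size, so these are assumptions.
- *Two patients.* Take concentration proportional to dose and to weight^−0.75, at 16 kg and 48 kg. The same-dose ratio is (48/16)^0.75 = 2.28. With the smaller child on 0.5 g and the larger on 1 g, the ratio seen is 2.28 × 0.5 = 1.14. With the doses reversed it is 2.28 × 2 = 4.56.
- *Simulation, Post-Amendment 3 Week 6, n = 25.* Concentration is proportional to dose and to weight^−0.5, CV 40%, with 15/35/50% of patients on 0.5/0.75/1 g. Slopes are in arbitrary concentration units per unit of log weight. Normalised to 0.75 g, the slope is about −1.5. Ignoring dose, it is −0.80 or −2.49 when the tendency to a higher dose has correlation +0.5 or −0.5 with weight, and −1.68 when unrelated. The last is a change of scale only: mean dose is 0.15 × 0.5 + 0.35 × 0.75 + 0.50 × 1 = 0.8375 g, and 1.5 × 0.8375/0.75 = 1.68.

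**The case against.** The strongest reply is that the SAP sends PK to a separate plan, which may already restrict to active gel and handle dose. That stands: the gap can be stated for the protocol and this SAP, not for every analysis the sponsor will run. But the protocol states a rule rather than staying silent, and a PK plan that followed it would inherit the problem.

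Analysis by visit already separates pre- from post-titration samples, and a placebo-free Post-Amendment 3 PK population is listed. Visit C in that population gives an age and weight comparison at one dose, including the youngest children. This also stands, but the protocol does not single out that comparison, and the Pre-Amendment 3 and Combined results remain affected.

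For concentration-response, placebo patients at about zero can be a useful anchor, and a spread of doses widens the range. Excluding them there is a matter of judgement. PK here is also sparse, descriptive and without a stated hypothesis test.

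A reader might infer more than the documents support:
- *All four levels are mixed throughout.* This happens only at Pre-Amendment 3 Weeks 4 and 6 and Combined Week 6.
- *Exposure in young children will be made to look like that in adolescents.* That needs smaller children to be titrated down more often. The documents tie titration to symptoms and side effects and report no relation to size; the bias could run either way.
- *Response-guided titration will flatten or reverse the Week 6 concentration-response slope.* This is possible, but nothing in the documents shows or sizes it.

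**Conclusion.** The concern holds for the protocol text. The placebo part needs no assumption about titration: about 50% of the Pre-Amendment 3 PK population and, at planned enrolment, about 40% of the Combined one would be placebo. By-visit means then fall to about 50% and 60% of the active-only values, and Pre-Amendment 3 age and weight slopes halve. In the Combined population the missing placebo below age 6 adds a separate distortion, up to an apparent two-fold difference where none exists. The net effect on a Combined slope is therefore not a simple shrinkage.

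These sizes assume that placebo concentrations are near zero and are entered as such. Section 11.7.7 does not say how values too low to measure are treated; if they were set to missing, most of the dilution of means would disappear.

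The dose part is conditional. Pre-Amendment 3 Weeks 4 and 6 and Post-Amendment 3 Weeks 6 and 14 mix 0.5 to 1 g/day. This biases age and weight slopes only if titrated dose is related to size, in an unknown direction; otherwise it changes scale and adds spread. Post-Amendment 3 Visit C is unaffected. The primary efficacy analysis is not touched.

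**What to change.** Amend Protocol 11.7.7, and the separate PK plan if it does not already say so:

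- (a) Restrict summaries of concentration and of the DEO to oxybutynin ratio, and the age, weight and body mass index regressions, to patients on active gel at sampling.
- (b) Tabulate concentrations by the dose in use at sampling.
- (c) In post-titration age, weight and body mass index regressions, use dose-normalised concentration or include dose as a term.
- (d) Name the pre-titration Week 2 samples (Visit 4 in patients on gel, and Visit C) as the main age and weight comparison.
- (e) For concentration-response, report the active-only result beside any analysis that includes placebo.

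If the PK plan already covers these, a cross-reference from 11.7.7 is enough. No new data are needed: dosing information goes on the eCRF (Protocol 9.4.2.2) and sample dates and times are recorded (Protocol 9.5.2). The cost is wording, a few table columns and smaller cells. With 25 Post-Amendment 3 patients over three doses, the average is about 8 per dose (25/3 = 8.3) before any split by age or sex.

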12 DATA HANDLING AND RECORDKEEPING

Electronic case report forms (eCRFs) will be designed and supplied by the sponsor. The eCRFs represent a record of the patient's experience in the study. The data recorded in the eCRFs must be supported by original (or source) medical records, as appropriate. Data recorded directly on the eCRFs (ie, no prior written or electronic record of data) will be considered source data.

Prior to enrolling a patient in the study, the investigator must review all laboratory reports used for screening procedures. Documentation of this review must exist in the source documents (ie, the investigator must sign/initial and date the laboratory reports, etc) to provide evidence of the review and to indicate the date on which the review took place. The investigator will keep a log of all *patients* who are screened and record the reason(s) for their exclusion. *e*CRFs should be completed only for *patients* who receive *study treatment*.

Completion and correction of *e*CRFs will follow the instructions *provided by the sponsor*. Completed eCRFs will be *electronically* signed and dated by the investigator.

12.1 Data Generation and Analysis

After the *site personnel complete* data entry, electronic error and logic checks will be conducted to identify missing, incorrect, and/or out-of-range values. Discrepancies will be *resolved through the system*.

12.2 Access to Source Documentation

The investigator agrees that the sponsor or its designated agents, the IRB, and the FDA or foreign regulatory agencies will have reasonable access to study source documentation for purposes of audit and review both during and after completion of the study. These monitoring visits provide the sponsor with the opportunity to evaluate the progress of the study; to verify the accuracy and completeness of eCRFs; to assure that all protocol requirements, applicable regulations, and investigator's obligations are being fulfilled; and to resolve any inconsistencies in the study records. All participating *patients* will be required to signify their approval to permit inspection of their medical records by representatives of the sponsor, the IRB, and the FDA and/or foreign regulatory agencies, as needed.

12.3 Retention of Data

In compliance with ICH guidelines, the investigator shall maintain adequate records for the study, including medical records, laboratory reports, consent forms, *study treatment* disposition records, safety reports, information regarding participants who discontinued, and other pertinent data. The investigator shall maintain these records for a period of at least 2 years after the last approval of a marketing application in an ICH region and until there are no pending or contemplated marketing applications in an ICH region, or at least 2 years have elapsed since the formal discontinuation of clinical development of the *study treatment*. These records should be retained for a longer period if required by the applicable regulatory requirements or by an agreement with the sponsor. The sponsor will inform the investigator/institution as to when these records no longer need to be retained.

13 OTHER INFORMATION

13.1 Financing and Insurance

Financing and insurance is addressed in a separate agreement.

13.2 Publication and Disclosure Policy

Publication and disclosure policy is addressed in a separate agreement.

13.3 Termination of the Study

If the study is terminated prematurely or suspended, all the appropriate IRB and regulatory authority (ies) will be promptly informed of the termination or suspension and will be provided the reason(s) for the termination or suspension. All obligations and responsibilities of the sponsor and the investigator under GCP, the US CFR, and the Declaration of Helsinki will remain in force if the study is terminated prematurely.

Appendix 1 Schedule of Events

Post-Amendment 3

	ScreeningPeriod	Open-Label Treatment Period				
	Visit A ¹	Visit B	Visit C	Visit D	Visit E	Visit F/ET
Evaluation:	-13 to -5 Days	Week 0	Week 2	Week 6	Week 10	Week 14
Informed Consent	X					
I/E Criteria	X	X				
Medical History	X	X				
Vision Assessment in Children < 8 years	x ²					
ConcomitantMedication	X	X	X	X	X	X
DemographicInformation	X					
Physical Examination	X					X
Height and Weight	X					
Vital Signs	X	X	X	X	X	X
12-Lead ECG	X					
Serum Chemistries	X					X
Hematology	X					X
Urinalysis	X	X ³				X
Urine Culture	X					
Urine Pregnancy Test ⁴	X			X		X
Urodynamics		X		X		
Dispense 2-day UrinaryDiary	X		X			
Collect 2-day UrinaryDiary		X		X		
Local ErythemaAssessment ^s			X	X	X	X
Adverse EventAssessment			X	X	X	X
Anticholinergic Questionnaire		X	X	X	X	X
Vision SymptomQuestionnaire		X	X	X	X	X
Collect PK Sample & Record Date/Time			X	X		X
Dose Titration (ifnecessary)			X			
Study TreatmentDispensing		X ⁶	X ⁶	X	X	
Study TreatmentCompliance			X	X	X	X

¹ All patients taking anticholinergic medications will be asked to discontinue treatment and complete a 3-day washout period (11-day washout period if the patient was previously taking solifenacin).

² Vision Assessment is required prior to or at the Baseline Visit for patients < 8 years of age, at the time of screening who have not received a vision screening assessment within the last 12 months prior to screening.

³ A urine sample for on-site urinalysis to determine presence of bacterial infection will be collected.

⁴ Urine pregnancy test will only be performed for females of childbearing potential.

⁵ Assessment for local erythema at application site

⁶ *Instruct patient/caregiver on study treatment application.*

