9.5.2.2 Visit **C** (Week 2 of Treatment) Dose Titration Opportunity

Patients will return to the clinic after 2 weeks of treatment for evaluation and a dose titration opportunity. Site personnel will perform the following activities:

- 1. *Perform study treatment* accountability.
- 2. Record concomitant medication use.
- 3. Measure *and record* vital signs (blood pressure, heart rate, respiratory rate, and temperature).
- 4. Query for adverse events.
- 5. Assess erythema/application site adverse events at most recent application site *and* document findings.
- 6. Dose titration: Based on the investigator's clinical judgment and assessment of bladder symptoms and treatment side effects, the dose can remain the same *at 0.75 g/day*, be increased to 1 g/*day*, or *can be* reduced to 0.5 g/*day*.
- 7. Collect blood sample for *PK* analysis and record the date and time of collection. Record *date* and time of last *2 days* gel applications (*visit date and day prior*).
- 8. Dispense *study treatment* kit for *the next 4* weeks of treatment and instruct patient/caregiver on *study treatment* application (Appendix 7).
- 9. Dispense 2-day urinary diary and remind patients that the urinary diary must be completed in the week prior to Visit D.
- 10. Instruct patient/caregiver to complete the anticholinergic questionnaire (Appendix 5) and the vision symptom questionnaire (Appendix 6).

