9.5.4 Early Termination Activities

Upon patient withdrawal/early discontinuation from the study, all evaluations scheduled at Visit F (Week 14 of treatment) should be completed at the termination visit. If the early termination visit occurs immediately after a visit in which a diary had been previously dispensed, the diary will be reviewed and collected.

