9.6.1 Urinary Diary

The urinary diaries will be completed by each patient/caregiver during the week before *Visit B and Visit D*. The 2-day urinary diary will be used to collect information for the parameters listed below. A sample urinary diary is *provided* in Appendix 3.

- Number of catheterizations per day
- Volume of urine collected at each (*after morning awakening*) catheterization
- Leakage incidents between catheterizations

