5.1.1.1.4 Missing Data

General missing data handling conventions for methodologies in Section 5.1.1.1.3 are summarized as follows:

Table 5-3 Missing Data Handling by Endpoint Type

Parameter type	Timing	Missing Data Handling
CFB ANCOVA	Treatment Period	 If missing a covariate: ○ Participant excluded If missing derived value at the specified post-baseline analysis visit: ○ Available cases (i.e., observed case [OC] analysis) ■ Participant excluded ○ Last observation carried forward (LOCF) ■ Participant included using LOCF-imputed value (last non-missing post-baseline value before the missing value is carried forward to impute the missing value). Baseline value will not be carried forward.

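### After Amendment 3, a child who stops before Week 2 has no on-treatment diary, and one who stops between Weeks 2 and 6 may return none, so LOCF cannot cover all early leavers

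*Protocol*

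**What the plan says.** **Collection.** In Protocol Appendix 1 the row "Dispense 2-day UrinaryDiary" is marked at Visits A and C, and the row "Collect 2-day UrinaryDiary" at Visits B and D. Neither is marked at Visit F/ET, and the Visit F task list (9.5.2.5) contains no diary. Section 9.6.1 describes the same two occasions, before Visit B and before Visit D.

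**Instructions to families.** At Visit C (9.5.2.2) the site is to "Dispense 2-day urinary diary and remind patients that the urinary diary must be completed in the week prior to Visit D". The sample diary (Appendix 3) is less specific: record two consecutive days ahead of the next visit and bring the diary along.

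**Early termination.** Section 9.5.4 says "all evaluations scheduled at Visit F (Week 14 of treatment) should be completed at the termination visit", and adds: "If the early termination visit occurs immediately after a visit in which a diary had been previously dispensed, the diary will be reviewed and collected".

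**Analysis.** SAP 5.1.1.1.4 (Table 5-3) carries forward the last non-missing post-baseline value and states "Baseline value will not be carried forward". SAP Table 5-1 admits a Post-Amendment 3 child to ITT only with at least one dose and at least one post-baseline primary value. Protocol 11.2 defines the same population by a baseline value alone, and says the LOCF visit imputes for non-completers and includes everyone in the corresponding ITT population. SAP Table 6-3 gives Post-Amendment 3 efficacy two windows, Baseline (Day 1 or earlier) and Week 6 (Day 29 or later).

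**The concern.** The primary endpoint is labelled Week 6 (LOCF), but only one post-baseline diary is scheduled after Amendment 3, and it is the Week 6 diary itself. LOCF has a value to use for an early leaver only if that diary happens to have been filled in early. Where it was not, the SAP drops the child from ITT, and the result describes those who stayed.

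If children leave because of poor effect or side effects, this favours gel in the Post-Amendment 3 one-sample test. It may also reach the placebo comparison: under SAP 5.1.1.3.1 the open-label gel patients are pooled with the randomised gel patients unless the Kolmogorov-Smirnov test gives p < 0.05. The two study parts would then enter one analysis with different chances of having a value to carry forward. A diary that was never issued cannot be recovered at the analysis stage.

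**Working it through.** **1. Who has a value, by time of stopping**

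| Child stops | Post-Amendment 3 | Pre-Amendment 3 (SAP Appendix 1) |
|---|---|---|
| Week 0 to 1 | No on-treatment diary issued | No on-treatment diary issued (first one at Visit 3, Week 1) |
| Week 1 to 2 | No on-treatment diary issued | Diary in hand, due at Visit 4 (Week 2) |
| Week 2 to 6 | Diary in hand; a value only if completed before the early-termination visit | Week 2 diary already collected |

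The period with no diary at all was about one week in both arms before Amendment 3. It is at least two weeks afterwards, in open-label gel patients only. Before Amendment 3 there was also a Week 2 value to carry forward to Week 6; now there is none.

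**2. Status of an early diary.** SAP Table 6-2 has a Pre-Amendment 3 Week 2 window of Days 2–28. Table 6-3 has no counterpart, so the SAP does not say whether an early-termination diary from before Day 29 counts for Week 6 (LOCF).

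**3. Planning figures.** Protocol 11.1 and SAP 5.1.2 give SD 28, gel change 25, placebo change 5, 48 per group, 93% power, and 90% power after 10% dropout. Two-sided 0.05 is assumed from the SAP's general convention.
- n = 48: SE = 28 × √(2/48) = 5.72; 20/5.72 = 3.50; power = Φ(3.50 − 1.96) = 93.8% (93.4% by noncentral t).
- n = 43 (48 less 10%): SE = 6.04; 20/6.04 = 3.31; power = 91.2% (90.6% by noncentral t).

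The stated figures reproduce and are not in dispute.

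**4. Number of children affected.** The documents give no Post-Amendment 3 dropout rate before Week 6, so I borrow the 10% planning rate: 25 × 0.10 = 2.5 leavers. If one third to one half stop before Visit C (an assumption), 2.5 × 1/3 = 0.8 to 2.5 × 1/2 = 1.3 children, or about one, certainly have no diary. The rest hold the Visit C diary.

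**5. Shift in the Post-Amendment 3 mean.** Let stayers average 25, leavers average c, and k of 25 be missing. Overstatement = k × (25 − c)/25.
- k = 1, c = 0: 1.0 point (all-enrolled mean 24.0).
- k = 2.5, c = 0: 2.5 points (22.5).
- k = 1, c = 5 (the placebo planning value): 0.8 points.
- k = 2.5, c = 5: 2.0 points.
- Leavers no different from stayers: 0.

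For scale, the standard error of the mean is 28/√25 = 5.6 points. One-sample power at a true change of 25 moves only from 99.0% (n = 25) to 98.3% (n = 23), so the issue is who is missing, not power.

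**6. Combined analysis.** If the planned 48 gel patients had all been enrolled before Amendment 3 (an assumption; actual enrolment is not given), pooled gel n = 48 + 25 = 73. Ignoring the covariate, and with c = 0, the shift in the gel mean is 25 × 1/73 = 0.3 to 25 × 2.5/73 = 0.9 points. Fewer Pre-Amendment 3 patients would mean less dilution.

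**The case against.** The strongest reply is that the plan already provides for most early leavers. Weeks 2 to 6 are two thirds of the period; a child leaving then holds a diary, Section 9.5.4 has it collected, and for that family the next visit named in Appendix 3 is the early-termination visit. This stands. A reader might infer that every child stopping before Week 6 has no diary, or that most such diaries will be blank. The first is contradicted by the Visit C dispensing, and nothing in the documents supports the second. What remains is a conflict between the Visit C reminder and the Appendix 3 instruction, with no text telling a leaving family which to follow.

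Second, the gap is not new. A Pre-Amendment 3 child of either arm who stopped before Visit 3 also had no on-treatment diary, and the SAP's Pre-Amendment 3 ITT likewise needs a post-baseline value. This also stands: Amendment 3 lengthened the gap and removed the Week 2 fallback.

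Third, the expectation that about 10 of 25 children complete 14 weeks might be read as heavy dropout. The synopsis says only a portion receive the additional 8 weeks, so children may finish at Week 6 by design, after the Visit D diary. The figure is not evidence of loss before Week 6.

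**Conclusion.** The point holds in a limited form. After Amendment 3, a child who stops before Visit C cannot have a post-baseline primary value, and a child who stops between Visits C and D may or may not have one. The SAP excludes those without, while the protocol says LOCF covers the whole ITT population; both cannot be met on this schedule.

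The likely effect is small: about 1 point on the Post-Amendment 3 mean if one early leaver is missing, up to 2.5 points at 10% dropout if no leaver returns a diary, and less when pooled. These figures rest on a dropout rate borrowed from the original design and on zero change in leavers. Neither is a Post-Amendment 3 figure from the documents, and the direction depends on leavers doing worse than stayers. Larger figures obtained by assuming 20% or 30% dropout have no source in the documents. This is a cheap improvement worth making, not a flaw that undermines the trial.

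**What to change.** **Protocol**
- Dispense a 2-day diary at Visit B as well as at Visit C.
- For patients who stop before Visit D, add diary collection to 9.5.4, the Visit F/ET list and the Appendix 1 F/ET column. Instruct them to complete it before the early-termination visit, and record whether gel was applied on the diary days.
- Make the Visit C reminder agree with Appendix 3 for leavers.

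**SAP**
- Add a Post-Amendment 3 efficacy window for Days 2–28 to Table 6-3, so that an on-gel early-termination diary counts for Week 6 (LOCF).
- Use off-gel diaries only in a sensitivity analysis, not in the primary LOCF value.
- Add a sensitivity analysis for leavers with no post-baseline diary, for example assigning zero change.
- Align the protocol and SAP definitions of the Post-Amendment 3 ITT population.

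**Cost.** One extra paper diary per child, a short amendment and an SAP edit. Leaving families have two more diary days, and some diaries will still not come back. If enrolment has closed, the SAP changes can still be made before database lock.
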